3.1.1.3 Clinical Event Committee – Hepatic external adjudication

Certain hepatic events will be adjudicated by external independent experts for severity and causal relationship with the trial medication in a blinded fashion. The events which will be reviewed will be defined in a charter. Events may either be defined by abnormal laboratory values and/or relevant adverse events or both. For example, assessments will be made for events of hepatic injury events, including liver enzyme elevations.

For qualifying events, relevant source documents generated from any medical evaluations of these events will be requested including laboratory values, histological analysis, results of ultrasound, CT, MRI, scintigraphy, hospital discharge letters, and medical reports from other physicians. All evaluations will be performed in a blinded fashion.

The tasks and responsibilities of the CEC will be specified in a charter. The CEC will maintain the adjudication results in writing.

3.2 DISCUSSION OF TRIAL DESIGN, INCLUDING THE CHOICE OF CONTROL GROUP(S)

This trial will investigate the efficacy and safety of an empagliflozin dosing regimen and one dose of linagliptin on top of standard treatment in children and adolescents with T2DM.

HbA1c as the primary endpoint has been demonstrated to be a reflection of the glycaemic control over the preceding 12 weeks and maintenance data over a period of approximately 6 months are requested by the different regulatory agencies. Therefore the primary endpoint for DINAMO™ is the change in HbA1c from baseline to the end of 26 weeks of randomised treatment.

For DINAMO™ Mono, the endpoint “occurrence of treatment failure” is selected to evaluate whether an early initial monotherapy is beneficial in children and adolescents with T2DM. A major component of the endpoint is “use of rescue medication”. Virtually all patients in DINAMO™ Mono who will not achieve the glycaemic goals defined in guidelines will

require rescue medication and will be classified as failure. Therefore, the study will inform whether the initial monotherapy can bring patients to glycemic target. Comparison with a placebo group is needed to better understand the failure rate of an “untreated population” in order to bring the results for empagliflozin and linagliptin into perspective. A similar endpoint was used in the TODAY study [R12-3961]. Since strict rescue criteria are defined for DINAMO™ Mono, the commonly used endpoint “HbA1c change from baseline” would not be informative. In the placebo group a high rate of rescue medication is expected, i.e. most patients randomised to placebo will benefit from metformin or insulin therapy. Since metformin and insulin are very effective especially in newly diagnosed patients, it is expected to observe no difference in HbA1c after 26 weeks in patients randomised to empagliflozin or linagliptin and placebo (on rescue treatment).

The randomised period is planned for 52 weeks in order to collect one year safety and efficacy data for empagliflozin and linagliptin in patients with T2DM aged 10-17 years (inclusive).

For the linagliptin treatment arm, one dose (i.e. linagliptin 5 mg) will be evaluated for safety over 52 weeks. For empagliflozin, two doses (i.e. empagliflozin 10 mg and 25 mg) will be evaluated as well as whether increasing the dose of empagliflozin 10 mg to 25 mg is beneficial to paediatric patients. So that, patients initially randomised to the empagliflozin 10 mg group who will not achieve an HbA1c target < 7.0% at Week 12 will be re-randomised at Week 14 to receive either empagliflozin 10 mg or empagliflozin 25 mg.

The rationale for the empagliflozin and linagliptin dose selection is described in [section 4.1.2](#).

Patients who were randomised to placebo will be re-randomised after 26 weeks to either linagliptin 5 mg or empagliflozin 10 mg or empagliflozin 25 mg. This reduces the duration of the placebo period in this trial to the requested minimum (26 weeks) and will ensure that all patients will receive active treatment for at least 26 weeks. Moreover, this will generate additional safety and efficacy data over 26 weeks of treatment for both empagliflozin doses and one linagliptin dose.

The design of this trial includes a 2-week open-label placebo run-in period; the intention of this period is to familiarise the patient with the procedures for study medication intake prior to randomisation, giving an opportunity for assessing the patient ability to be compliant with the study medication intake. This is of particular importance within the paediatric population where adherence to medical regimens is often less than desired. The run-in period will therefore ensure that only patients who are likely to be compliant are exposed to the study drugs.

The 3-week follow-up period is considered to be sufficient, as previous studies with empagliflozin and linagliptin have shown that its' PD effect only extends to about 3 and 7 days after the last dose. Furthermore, it will allow for the assessment of reversibility of unexpected long-term side effects.

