
planned end of the study. A descriptive Log-rank test will compare the linagliptin group and the empagliflozin group versus the placebo group individually up to Week 26.
 
The change in HbA1c from baseline to the end of 26 week will be analysed based on a REML approach using MMRM to assess the effectiveness and efficacy.
 
The change in HbA1c from baseline to the end of 26 week will also be analysed using an ANCOVA model including treatment as a fixed classification effect, baseline HbA1c as a linear covariate, and age as a categorical covariate. The secondary endpoints of change in FPG, body weight, SBP and DBP from baseline to the end of 26 week will be analysed in the same way as DINAMO™ with the DINAMO™ Mono data.
 
The proportion of patients who achieve HbA1c < 7.0% and < 6.5% at the end of 26 week will be determined per treatment group and the risk difference of active treatments versus placebo will be determined and assessed by an exact 2-sided 90% confidence interval.
			

FLOW CHART

Trial Periods	Screening	Placebo Run-in ¹	Randomised treatment period ⁴								Follow-up
	1A	1B	2 ²	3	4A	4B ³	5 ²	6	7	8 ² EOT ⁵	9 ¹³
Days calculated from the day of first (randomised) treatment	-21 to -14	-14	Day 1	29	85	99	183	211	295	365	386
Weeks from date of first randomised treatment			(**)	4	12	14	26	30	42	52	55
Time window for visits	+7 days ¹¹	+7 days ¹²	none	±7 days	±7 days	±7 days	±7 days	±7 days	±7 days	±7 days	+7 days
Informed consent and assent (*)	X										
Demographics	X										
Medical history	X										
Physical examination		X	X				X			X	X
Tanner staging (modified) ⁶			X				X			X	
Vital signs (seated) ¹⁴		X	X	X	X		X	X	X	X	X
12 lead-ECG		X					X			X	
Safety Laboratory tests ¹⁴	X ⁷		X ²	X	X		X ²	X	X	X ²	X
HbA1c ¹⁴	X		X	X	X		X	X	X	X	
PK blood sampling							X ⁸			X ⁸	
Fasting plasma glucose (FPG)			X ²				X ²			X ²	

FLOW CHART (cont.)

Trial Periods	Screening	Placebo Run-in ¹	Randomised treatment period ⁴								Follow-up
			2 ²	3	4A	4B ³	5 ²	6	7	8 ² EOT ⁵	
Visit	1A	1B	2 ²	3	4A	4B ³	5 ²	6	7	8 ² EOT ⁵	9 ¹³
Days calculated from the day of first (randomised) treatment	-21 to -14	-14	Day 1	29	85	99	183	211	295	365	386
Weeks from date of first randomised treatment			(**)	4	12	14	26	30	42	52	55
IGF-1, IGF-BP3 and markers of bone turnover ¹⁴			X	X ⁹			X	X ⁹		X	X
DPP-4 activity			X ¹⁰								
Pregnancy test ¹⁴	X		X	X	X		X	X	X	X	
Auto-antibodies for diabetes (IA-2 and GADA)	X										
Serum C-peptide	X		X ²				X ²			X ²	

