6.2.3 Follow Up Period and Trial Completion

For patients who complete treatment as planned, a follow-up (FUP) visit should be planned 3 weeks after last trial drug administration. For detailed description of the trial procedures at the FUP visit, please refer to the Flow Chart.

Trial completion

The trial completion eCRF end-of-study page has to be filled-in when the patient has terminated the trial.

The end of the trial is:

- At the end of the follow-up visit for patients who have completed the trial on treatment as planned;
- After the early unscheduled end of treatment (EOT) visit, if a patient did not agree to come to the remaining planned study visits and also disagrees to be contacted at all;
- After the Visit 9/FUP visit (in person or by telephone) at Week 55, for patients who discontinued drug early but agreed to come to the remaining planned study visits, or agree to be contacted/allow access to medical records.

Patients who prematurely discontinued trial medication

Patients who prematurely discontinue study drug (refer to [section 3.3.4](#)) before the planned end of treatment at Visit 8, should come to the clinic as soon as possible after last drug intake for an immediate unscheduled early EOT visit. The reason for premature trial drug discontinuation must be documented in the eCRF. For detailed description of the trial procedures at this visit, please refer to the [Flow Chart](#).

In addition patients will be encouraged to attend all subsequent planned visits despite not being under treatment anymore and perform all study procedures except pharmacokinetic sampling.

Study assessments may be omitted if a patient is willing to return to the pre-defined study visits, with exception of blood drawing for safety lab tests, HbA1c and FPG, body weight, blood pressure and collection of adverse events, and concomitant therapy.

The need for coming to future visits in case of premature discontinuation of trial medication will be explained to patients prior to their participation in the trial.

Vital status information

In case of early discontinuation of trial medication, if the patient does not agree to come to future visits as planned, every attempt will be made to get information on vital status at Week 55 after his/her randomisation.

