7.3.6 Safety analyses

Adverse events will be coded using the Medical Dictionary for Regulatory Activities (MedDRA) coding dictionary. Standard BI summary tables and listings will be produced. In general, safety analyses will be descriptive in nature and will be based on BI standards. No hypothesis testing is planned.

Statistical analyses and reporting of adverse events will concentrate on treatment-emergent adverse events. To this end, all adverse events occurring between start of treatment and end of the residual effect period will be considered 'treatment-emergent'. The residual effect period is defined as 7 days after the date of the last dose of trial medication. Adverse events that start before first drug intake and deteriorate under treatment will also be considered as 'treatment-emergent'. All AEs occurring before first study medication intake will be assigned to 'pre-treatment' and all AEs occurring after last study medication intake plus 7 days will be assigned to 'post-treatment'.

Frequency, severity, and causal relationship of adverse events will be tabulated by system organ class and preferred term after coding according to the current version of MedDRA.

Laboratory data will be analysed both quantitatively as well as qualitatively. The latter will be done via comparison of laboratory data to their reference ranges. Values outside the reference range as well as values defined as clinically relevant will be highlighted in the listings. Treatment groups will be compared descriptively with regard to distribution parameters as well as with regard to frequency and percentage of patients with abnormal values or clinically relevant abnormal values.

Vital signs, physical examinations, or other safety-relevant data observed at screening, baseline, during the course of the trial and at the end-of-trial evaluation will be assessed with regard to possible changes compared to findings before start of treatment.

The safety analyses will be performed using the following population set and randomised study treatment combinations according to the defined period, separately for DINAMO™ and DINAMO™ Mono.

- **Comparison vs. placebo:** All patients in the TS will be included in the safety analyses up to Week 26 presented by placebo, linagliptin 5 mg and empagliflozin pooled.

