#### Observed cases – Rescue observed cases (OC-ROC) analysis

Only the available data that were observed while patients were on-treatment will be considered. Any values taken after rescue medication intake will be kept. Any values collected after treatment discontinuation will be set to missing.

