#### 6.7 BASELINE, TIME WINDOW, AND CALCULATED VISITS

The term “baseline” refers to the following definitions according to the individual analysis period.

- *Study baseline*: Last observed measurement prior to administration of any initially randomised study medication at Day 1.
- *Titration baseline*: Last observed measurement prior to administration of the re-randomised study medication for the initial empagliflozin patients at Week 14. If last observed measurement is after rescue medication then there is no titration baseline for OC analysis.
- *Safety extension baseline*: Last observed measurement prior to administration of the re-randomised study medication for the initial placebo patients at Week 26.

Note: On or prior to date of randomisation will be used, instead of prior to date of drug administration, for randomised patients who have not taken any blinded study drug.

Both date and time of administration of the randomised study medication are expected to be recorded at Day 1, Week 14 and Week 26. In the determination of baseline for a parameter, if the parameter of interest:

- is collected with date and time: both date and time are used in the calculation of ‘last observed measurement prior to administration’. If the dates and times are equal, the parameter will be determined to be prior to administration.

- is collected with only date: the dates are equal, the parameter will be determined to be prior to administration.

The exception to this rule, is HbA1c, whereby even though time of sample is collected, it will be handled as if it was collected only with date.

Measurements taken after the first intake of randomised study drug will be considered on-treatment values if they have been obtained up to the end of the endpoint specific follow-up period as defined in [Table 6.7: 1](#).

Table 6.7: 1 Endpoint specific follow-up period for the assignment to treatment phase

Endpoint	Last day of assignment to treatment phase (days after study drug stop date)
Efficacy	
HbA1c	7
FPG	1
Body weight	1
BMI z-score	1
Blood pressure (systolic, diastolic)	1
UACR	7
Safety	
Adverse events	7
AESI Hepatic injury 	30
AESI Lower limb amputation	End of study
Safety laboratory measurements	7
AST/ALT/TBILI 	30
Pulse rate	1
C-peptide	1
Tanner staging	1

[1] Refers to a specific safety analysis including all hepatic injuries with an onset date up to 30 days after the study treatment stop.

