[2] Refers to a specific safety analysis on elevated liver enzymes, for which events with an onset date up to 30 days after the study treatment stop will be included in the analysis. See [Section 7.8.2.2](#).

Measurements taken after the last intake of study drug and end of the endpoint specific follow-up period will be considered post-treatment values. In efficacy analyses, the words off-treatment and post-treatment are used synonymously.

Efficacy and safety measurements will be assigned to visits based on time windows around the planned visit dates. These time windows are defined based on the planned number of days after the date of first administration of study drug (see [Table 6.7: 2](#)).

Table 6.7: 2 Time windows for efficacy and safety measurements at scheduled visits after randomisation

Visit number	Visit label	Planned days on treatment	Planned days after randomisation	Time window (actual days on treatment)	
				Start	End A
2	Baseline	1	0 C	NA	1 B
3	Week 4	29	28	2	56
4A	Week 12	85	84	57	91
4B	Week 14	99	98	92	140 B
5	Week 26	183	182	141	Max(Day 141, Visit 5 drug intake date, Min(Day 210, Visit 6 date – 1 day))
6	Week 30	211	210	Max(Day 141, Visit 5 drug intake date, Min(Day 210, Visit 6 date – 1 day)) + 1 day	225
7	Week 42	295	294	226	329
8	Week 52 / EoT	365	364	330	Study drug stop date + X days

A In case of premature discontinuation of the study drug an early EoT visit has to be performed. Measurements from the early EoT visit will be assigned to the appropriate visit according to the table. Patients will then be asked to continue in the study according to the visit schedule. Post-treatment measurements will be assigned to visits in the same manner.

B Only values taken prior to the start of treatment at Day 1, Week 14 and Week 26, with randomised study drug can be considered study baseline, titration baseline and safety extension baseline accordingly. Time windows will be used for assignment of measurements to scheduled visits.

C Reference day (day 0) is day of randomisation

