#### 7.8.2.5 Biomarkers

Descriptive statistics will be summarised over time up to Week 26 by TG1 and up to Week 52 by TG5 on the standard units for PINP, IGF-1, and IGF-BP3.

Descriptive statistics by sex and tanner stage category version 2, see [Table 6.4:1](#) for the category, will be summarised over time up to Week 26 by TG1 and up to Week 52 by TG5 on the standard units for PINP, NTx, IGF-1, IGF-BP3.

Descriptive statistics of DPP-4 activity pre-dose measurement at Day 1 will be summarised by TG1 on the standard unit.

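### Visit 9, three weeks off drug, has no analysis window in the SAP, so its bone-marker, IGF, haematocrit and renal values are listed but reach no visible summary, although reversibility is a stated reason for the follow-up period

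*Protocol*

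**What the plan says.** **Purpose.** Protocol 3.2 gives two reasons for the follow-up period. The drugs' pharmacodynamic effect has worn off by then, and "it will allow for the assessment of reversibility of unexpected long-term side effects". Protocol 7.3.6 adds that vital signs, physical examinations and other safety-relevant data "at the end-of-trial evaluation will be assessed with regard to possible changes compared to findings before start of treatment". For patients who complete treatment, Protocol 6.2.3 places the end of the trial at the follow-up visit, so for them this evaluation is Visit 9.

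**Collection.** Under Protocol 6.2.3, "a follow-up (FUP) visit should be planned 3 weeks after last trial drug administration". The flow chart marks Visit 9 for safety laboratory tests, vital signs, weight and the row "IGF-1, IGF-BP3 and markers of bone turnover". The footnote that omits IGF-1 and IGF-BP3 is attached to Visits 3 and 6, not to Visit 9. Height is not measured at Visit 9.

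**Analysis.** SAP Table 6.7: 2 covers both efficacy and safety measurements. Its last row is Visit 8 (Week 52 / end of treatment), which closes at "Study drug stop date + X days", with X taken from Table 6.7: 1. SAP 7.8.2 and Table 6.3: 1 put the laboratory, renal and biomarker summaries on the OC-ROC data selection. Under SAP 6.6.1 that selection keeps only on-treatment observations: "Any values collected after treatment discontinuation will be set to missing". SAP 7.8.2.5 states the reach of the biomarker tables: "Descriptive statistics will be summarised over time up to Week 26 by TG1 and up to Week 52 by TG5".

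**The concern.** The protocol collects off-drug samples from children and adolescents and names reversibility as a purpose, but the SAP's rules keep those samples out of the group-level tables. Suppose bone turnover, IGF-1, haematocrit or eGFR shifts during treatment. The natural next question is whether it returns once the drug stops. The trial will hold the data, but the report as planned would not summarise them by treatment. The protocol uses this kind of evidence itself: Section 1.2.1 interprets the adult eGFR effect partly through its return to baseline 4 weeks after discontinuation.

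This is more than missing detail. Followed as written, the rules exclude the values.

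**Working it through.** The plan gives no figure to reproduce. The check compares the timing of Visit 9 with the end of the last analysis window, then traces each measurement to its planned summary.

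**Inputs.** Visit 8 is Day 365 (±7 days) and Visit 9 is Day 386 (+7 days), both from the flow chart. From SAP Table 6.7: 1, X is 7 days for safety laboratory measurements, 1 day for weight, blood pressure and pulse, and 30 days for AST, ALT and total bilirubin. Bone markers, IGF-1 and IGF-BP3 have no line of their own. I treat them as safety laboratory, because Protocol 5.3.3 and SAP 7.8.2 both place them there. The last dose is taken to be at Visit 8, as the flow chart shows.

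**Step 1: days off drug at Visit 9.**
- As planned: 386 − 365 = 21 days, or 393 − 365 = 28 days at the end of the Visit 9 window.
- Shortest, with Visit 8 late and Visit 9 on its original day: 386 − 372 = 14 days.
- Longest, with Visit 8 early and Visit 9 late: 393 − 358 = 35 days.

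**Step 2: does Visit 9 fall inside the last window (365 + X)?**

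| Measurement | X | Window closes | Visit 9 at Day 386 |
|---|---|---|---|
| Safety laboratory, including bone markers, IGF, haematocrit, creatinine | 7 | Day 372 | 14 days after closing |
| Weight, blood pressure, pulse | 1 | Day 366 | 20 days after closing |
| AST, ALT, total bilirubin | 30 | Day 395 | inside |

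Even the shortest gap, 14 days, exceeds both 7 and 1. Outside the three liver tests, every Visit 9 value is post-treatment with no analysis visit. The liver tests are covered at gaps of 14, 21 and 28 days, but not at the extreme of 35.

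**Step 3: where would each measurement be summarised?**
- *PINP, NTx, IGF-1, IGF-BP3* (SAP 7.8.2.5): OC-ROC, to Week 26 or Week 52.
- *Haematocrit, the remaining bone markers and NTx again* (7.8.2.1): baseline, last on-treatment value, and values by analysis visit. Visit 9 is neither on treatment nor an analysis visit.
- *Creatinine and eGFR* (7.8.2.4): OC-ROC, to 26 or 52 weeks.
- *Heart rate* (7.8.3): OC-ROC, to Week 52.
- *Weight, systolic and diastolic pressure* (7.5.2.1): OC-AD and OC, to Week 26. OC-AD keeps post-treatment values, so off-drug readings from patients who stop before Week 26 do enter the model. Visit 9 readings are absent because the visible analyses end at Week 26 and the window table ends at Visit 8, not because of OC-ROC.

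One might argue that treatment discontinuation in the OC-ROC rule means only premature stopping. That does not rescue Visit 9, because the same definition first limits the data to on-treatment observations.

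**The case against.** **The protocol sentence is narrow.** It speaks of unexpected side effects and promises no table of routine marker means. Clinically relevant laboratory or vital-sign changes become adverse events, which are followed until resolved, chronic or stable (Protocol 5.3.6.2) and tabulated by outcome (SAP 7.8.1.3). Liver tests are followed for 30 days. This stands as partial coverage. It does not reach a group shift in PINP, NTx, IGF-1, haematocrit or eGFR that no investigator reports as an event. It is also fair that Protocol 7.3.6 deals with laboratory data in a separate paragraph and fixes no format for the end-of-trial comparison.

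**The values are reported.** SAP 7.8.2 puts individual laboratory results in listings. That is correct, but a listing gives no change by treatment.

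**The public SAP is incomplete.** Sections 5.3, 6.4, 7.4.1.3, 7.6 and 9 cannot be seen. For weight, blood pressure and UACR, a follow-up summary could exist there. For bone markers, IGF, haematocrit and creatinine/eGFR the governing sections are visible, so the point is firmest for these.

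**The off-drug change is hard to interpret.** Placebo patients are re-randomised to active drug at Week 26, so Visit 9 has no concurrent placebo group. The adult eGFR result had one through the same off-drug period. Only Visits 2, 5 and 8 are fasting (Protocol 6.2.2), while Protocol 5.3.3 specifies fasting samples for IGF-1 and IGF-BP3. This stands as a limit on what the table can show. It is not a reason to leave the data unsummarised.

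**Conclusion.** The mismatch is real and modest. Visit 9 has no analysis window. Its bone-marker, IGF-1, IGF-BP3, haematocrit and creatinine/eGFR values are listed but appear in no visible summary, although the protocol gives reversibility as a reason for the period. It should be corrected because the correction is cheap. No hypothesis, estimand or planned on-treatment comparison changes.

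The documents do not support four stronger readings that a reader might infer:
- *That the off-drug data are discarded.* Laboratory values are listed, liver tests are covered to 30 days, and adverse events are tabulated by outcome.
- *That the SAP sets all post-treatment values to missing.* OC and OC-ROC do; OC-AD does not.
- *That Visit 9 weight and blood pressure certainly reach no summary.* They have none in the visible text, but the non-public sections cannot be excluded.
- *That every child contributes.* About 170 (150 + 20) is the planned enrolment and only a ceiling. Early stoppers may have Visit 9 by telephone, and the visit may be remote because of COVID-19.

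The conclusion assumes that the last dose is at Visit 8 and that bone and IGF markers take the 7-day safety laboratory limit.

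**What to change.** 1. Add a Visit 9 row to SAP Table 6.7: 2, with planned Day 386 and opening after study drug stop + X days.
2. Exempt that row from the OC-ROC rule for this one purpose, leaving the on-treatment tables unchanged.
3. Add one descriptive table by last treatment taken, in patients treated to Visit 8 who have a Visit 9 sample. Show baseline, Visit 8, Visit 9, and the changes to Visit 9 from baseline and from Visit 8, with the number of patients contributing. Cover bone markers, IGF-1, IGF-BP3, haematocrit and creatinine/eGFR. Compute Visit 9 eGFR with the Visit 8 height. Include weight and blood pressure if they are not already summarised elsewhere. State which baseline applies to patients who began on placebo, since SAP 6.7 defines both a study and a safety extension baseline.
4. Footnote the limits: no placebo group after Week 26, a non-fasting visit (which matters for IGF, and for lipids if they are added), and fewer patients because of remote visits.

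The restriction to patients treated to Visit 8 keeps out early stoppers, whose time off drug is longer. The cost is one table row and one descriptive output from data already collected, with no multiplicity consequence. The price is interpretive: the table can describe a return towards baseline but cannot attribute it to stopping the drug.
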